7.4. Dose Escalation for ATRA and Study Stopping Rules

The phase 1b portion of the study will follow a 3+3 dose escalation design to evaluate Dose Level 1 (35.5 mg/m²/day) followed by Dose Level 2 (45 mg/m²/day) of ATRA in combination with Dara + Pom + dex for DLTs and to determine the MTD for further assessment in phase 2.

Patients will be enrolled in cohorts of 3 and assessed for DLTs over a 28-day period. In each dose level, the second and third patients can be dosed concurrently once the first patient in the cohort has gone uneventfully through the Day 8 visit. If it is necessary to enroll more than 3 patients in a cohort, and there have not been any TEAEs in the previously dosed patients in that cohort, these new patients can be enrolled concurrently.

If none of the patients in a cohort of 3 patients exhibits a DLT during the 28-day cycle, then the dose may be escalated for the next cohort of 3 patients. If 1 patient in a cohort of 3 patients exhibits a DLT, then that cohort will be expanded to a total of 6 patients. If 2 or more patients in a cohort of 3 patients exhibit a DLT, then that cohort will be deemed to have exceeded the MTD, and dose escalation will be stopped.

If the dose cohort below that at which the MTD is exceeded has enrolled only 3 patients, then 3 additional patients will be enrolled at that dose level. The MTD is defined as the highest dose with a cohort of 6 patients having no more than 1 patient with a DLT. For the cohort expansion, 3 patients will only be enrolled sequentially if a DLT observed in the initial cohort was life-threatening, it appeared before the Day 8 visit and/or the clinical team consider that based on the observed toxicity is prudent to stagger the enrollment. Sequential enrollment is not required in case of de-escalation or if no DLT was observed in the first 3 patients in a cohort.

During phase 1b dose escalation, patients who miss one or more scheduled Cycle 1 doses of ATRA for reasons other than a DLT will be replaced.

Before initiating the dosing of the next cohort or opening a new schedule, when safety data are available for all patients in the current cohort, key safety data will be reviewed and evaluated by the study team consistent of investigators who will review the safety of all treated patients and make decisions regarding dose escalation. In addition, further changes to the dose escalation scheme may be considered. All decisions will be documented in writing. Any decision to modify the dose escalation scheme in a direction that increases the already approved frequency of administration or dose escalation steps, will be communicated to institutional review boards (IRBs) and the protocol amended accordingly.

7.5. Dose Modification

Management of Infusion-related Reactions and Local Injection-site Reactions of Daratumumab-SC

Infusion-related Reactions (IRRs)

Infusion-related reactions (IRRs) are systemic reactions related to daratumumab administration. Participants should be observed carefully during daratumumab administrations. Trained study staff at the clinic should be prepared to intervene in case of any IRRs, and resources necessary for resuscitation (e.g., agents such as epinephrine and aerosolized bronchodilator, medical equipment such as oxygen tanks, tracheostomy equipment, and a defibrillator) must be available at the bedside. Attention to staffing should be considered when multiple participants will be dosed at the same time. If an IRR develops during Dara SC administration, then the administration should be temporarily interrupted. Participants who experience AEs during Dara-SC administration must be treated for their symptoms. Participants should be treated with paracetamol (acetaminophen), antihistamine, or corticosteroids, as needed. Intravenous saline may be indicated. For bronchospasm, urticaria, or dyspnea, participants may require antihistamines, oxygen, corticosteroids, or bronchodilators. For hypotension, participants may require vasopressors. In the event of a life-threatening IRR (which may include pulmonary or cardiac events) or an anaphylactic reaction, Dara-SC should be discontinued.

Infusion-related Reactions Grade 1 or Grade 2:

If the investigator assesses a Grade 1-2 IRR to be related to administration of study intervention, then the Dara-SC administration should be interrupted. When the participant's condition is stable, Dara-SC administration may be restarted at the investigator's discretion. Refer to the SIPPMM for further details regarding continuation of Dara-SC administration.

If the participant experiences a Grade 2 or higher event of laryngeal edema, or a Grade 2 or higher event of bronchospasm that does not respond to systemic therapy and does not resolve within 6 hours from onset, then the participant must be permanently discontinued from Dara-SC treatment.

Infusion-related Reactions Grade 3 or Higher:

For IRR AEs (other than laryngeal edema or bronchospasm) that are Grade 3, the Dara-SC administration must be stopped, and the participant must be observed carefully until resolution of the AE or until the intensity of the event decreases to Grade 1, at which point the Dara-SC administration may be restarted at the investigator's discretion. Refer to the SIPPMM for further details regarding continuation of Dara-SC administration.

If the intensity of the AE returns to Grade 3 after restart of the Dara-SC administration, then the participant must be permanently discontinued from Dara-SC treatment.

For IRR AEs that are Grade 4, the Dara-SC administration must be stopped, and the participant permanently discontinued from Dara-SC treatment.

Recurrent Infusion-related Reactions:

If a Grade 3 IRR (or Grade 2 or higher event of laryngeal edema, or a Grade 2 or higher event of bronchospasm) recurs during or within 24 hours after a subsequent Dara-SC administration, the participant must be permanently discontinued from Dara-SC treatment.

Injection Site Reactions:

In clinical studies, SC administration of daratumumab was associated with local injection site reactions, such as induration and erythema, in some subjects. The reactions usually resolved within 60 minutes. Local injection-site reactions should be managed per institutional standards.

Recommended Concomitant Therapy:

- Prophylaxis for Herpes Zoster Reactivation:
- Prophylaxis for herpes zoster reactivation is recommended during the Treatment Phase, as per institutional guidelines. Initiate antiviral prophylaxis to prevent herpes zoster reactivation within 1 week after starting study treatment and continue for 3 months following study treatment. Acceptable antiviral therapy includes acyclovir (eg 400 mg given orally 3 times a day, or 800 mg given orally 2 times a day or per institutional standards), famcyclovir (eg, 125 mg given orally, twice a day or per institutional standards), or valacyclovir (eg, 500 mg given orally, twice a day or per institutional standards), initiated within 1 week after the start of study drug.
- Management of Hepatitis B Virus Reactivation:
- Primary antiviral prophylaxis is permitted as per local standard of care. Per protocol, HBV DNA testing by PCR is mandatory for participants at risk for HBV reactivation.

In patients who develop reactivation of HBV while on study treatment, suspend treatment with study treatment and any concomitant steroids, chemotherapy, and institute appropriate treatment.

Resumption of study treatment in patients whose HBV reactivation is adequately controlled should be discussed with physicians with expertise in managing HBV

Daratumumab Dose Modification

Individual dose modification of daratumumab is not permitted, but dose delay is recommended as the primary method for managing daratumumab-related toxicities, as described in Section 7.5.

Daratumumab-related Toxicity Management

Refer to Section 7.5 for details on management of daratumumab injection-related reactions.

If any of the following criteria are met and the toxicity is more than expected for pomalidomide or underlying multiple myeloma, daratumumab injection must be held to allow for recovery from toxicity. If attribution is unclear, then daratumumab should be held until recovery from toxicity as noted below.

The criteria for a dose delay are:

- Grade 4 hematologic toxicity, except for Grade 4 lymphopenia
- Grade 3 thrombocytopenia with bleeding
- Febrile neutropenia
- Grade 4 Neutropenia with infection, of any grade
- Grade 3 or higher non-hematologic toxicities with the following exceptions:
 - Grade 3 nausea that responds to antiemetic treatment within 7 days
 - Grade 3 vomiting that responds to antiemetic treatment within 7 days
 - Grade 3 diarrhea that responds to antidiarrheal treatment within 7 days
 - Grade 3 fatigue that was present at baseline or that lasts for <7 days after the last administration of daratumumab
 - Grade 3 asthenia that was present at baseline or that lasts for <7 days after the last administration of daratumumab

Administration of daratumumab may be restarted upon recovery from toxicity to Grade 2 or baseline, with the exception that Grade 2 laryngeal edema or Grade 2 bronchospasm must be fully recovered. Other than on Day 1 of a cycle, if any “within-cycle” daratumumab administration does not commence within the prespecified window of the scheduled administration date (Table 3), then the dose will be considered a missed dose. Administration may resume at the next planned dosing date.

Table 3: Daratumumab-related Toxicity Management

Daratumumab Dosing Frequency	Dose Missed	Dosing Resumption
Weekly	>3 days	Next planned weekly dosing date

Table 3: Daratumumab-related Toxicity Management

Daratumumab Dosing Frequency	Dose Missed	Dosing Resumption
Every 2 weeks	>7 days	Next planned every-2-weeks dosing date
Every 4 weeks	>21 days	Next planned every-4-weeks dosing date

A missed dose will not be made up. Delay of Day 1 drug dosing in any given cycle should not result in a skipped dose but should lead to a delay of the entire cycle instead. A minimum of 4 days between daratumumab doses must be observed.

If a dose is delayed, then the dates of all subsequent doses must be adjusted. If a dose delay occurs, then blood samples should be collected on the actual day of study drug administration, not on the original scheduled drug administration day. Any adverse event deemed to be related to daratumumab that requires a dose hold of more than 28 days will result in permanent discontinuation of daratumumab, unless, upon consultation with the sponsor and the review of safety and efficacy, continuation is agreed upon.

Daratumumab Interruption or Missed Doses

A daratumumab dose that is held for more than the permitted time (Table 3) from the per-protocol administration date for any reason other than toxicities suspected to be related to daratumumab should be brought to the attention of the sponsor at the earliest possible time. Patients whose dose is delayed or missed for 3 or more consecutive doses should be withdrawn from study treatment, unless, upon consultation with the sponsor and the review of safety and efficacy, continued treatment is agreed upon.

Pomalidomide related toxicities

Table 4: Dose Modification Instructions for Pomalidomide

Toxicity ^a	Dose Modification
Neutropenia Grade 4 neutropenia (ANC < 500/ μ L) or Febrile neutropenia (ANC < 1,000/ μ L with a single temperature of > 38.5 °C or a sustained temperature of \geq 38 °C for more than one hour)	Withhold the dose and follow CBC weekly. If the subject was not receiving GCSF therapy, GCSF therapy may be started at the discretion of the treating physician. When dosing is resumed, the dose of POM may be maintained if neutropenia was the only POM-related toxicity requiring a dose modification and GCSF treatments are continued. Otherwise, decrease by one dose level. Note grade 4 neutropenia, ANC must be \geq 500/ μ L to restart dosing.

	For febrile neutropenia, ANC must be $\geq 1,000/\mu\text{L}$ to restart pomalidomide dosing at 1 mg less than the previous dose.
Thrombocytopenia Grade 4 thrombocytopenia (Platelets $< 25,000/\mu\text{L}$)	Withhold the dose and follow CBC weekly. Dosing may resume at one dose level lower once the platelet count has recovered to $\geq 50,000/\mu\text{L}$.
Rash, Grade 3	Withhold dose for remainder of cycle. Decrease by one dose level when dosing restarted at next cycle (rash must resolve to \leq Grade 1 before restarting dosing).
Rash, Grade 4 or Blistering	Discontinue subject from study treatment.
VTE \geq Grade 3	Withhold dose for remainder of cycle. Assess anticoagulation treatment. Maintain dose level when dosing restarted at next cycle at discretion of treating physician. For Grade 4 VTE, discontinue pomalidomide treatment.
Other \geq Grade 3 POM-related ^b adverse events	Withhold dose. Decrease by one dose level when dosing restarted (adverse event must resolve to \leq Grade 1 before restarting dosing). For Grade 4 non-hematologic adverse events, discontinue pomalidomide treatment.

ANC = absolute neutrophil count; GCSF = granulocyte colony-stimulating factor; POM = Pomalidomide; VTE = venous thromboembolism.

^a If recovery from toxicities is prolonged beyond 14 days, then the dose of POM will be decreased by one dose level when dosing is restarted.

^b For Grade 3 or 4 AEs that are not considered to be related to study drug, the treating physician should consult with the sponsor institution for dose interruptions and reductions.

Table 5: Pomalidomide Dose Reduction Steps

Dose Level ^a	Pom Dose reduction
Starting dose	4 mg
Dose Level -1	3 mg
Dose Level -2	2 mg
Dose Level -3	1 mg

^a The minimum permitted dose level for POM is 1.0 mg. No dose re-escalation is permitted for Pomalidomide.

Table 6: Dose Reductions for Dexamethasone-related Toxicities

Toxicity ^a	Dex Dose Modification
Dyspepsia = Grade 1-2	Maintain dose and treat with histamine (H2) blockers or equivalent. Decrease by one dose level if symptoms persist.

Dyspepsia \geq Grade 3	Withhold dose until symptoms are controlled. Add H2 blocker or equivalent and decrease one dose level when dose restarted.
Edema \geq Grade 3	Use diuretics as needed and decrease dose by one dose level.
Confusion or mood alteration \geq Grade 2	Withhold dose until symptoms resolve. When dose restarted, decrease dose by one dose level.
Muscle weakness (steroid myopathy) \geq Grade 2	Withhold dose until muscle weakness \leq Grade 1. When dose restarted decrease dose by one dose level.
Hyperglycemia \geq Grade 3	Decrease dose by one dose level. Treat with insulin or oral hypoglycemic agents as needed.
Acute pancreatitis	Discontinue subject from Dex treatment regimen.
Other \geq Grade 3 Dex-related adverse Events	Stop Dex dosing until the adverse event resolves to \leq Grade 2. Decrease by one dose level when Dex dosing is resumed.

^a If recovery from toxicities is prolonged beyond 14 days, then the dose of Dex will be decreased by one dose level when dose is restarted.

Table 7: Dexamethasone Dose Reduction Steps

Dose Level	≤ 75 years old	>75 years old
Starting Dose	40 mg	20 mg
Dose Level -1	20 mg	12 mg
Dose Level -2	10 mg	8 mg

ATRA will be administered in a divided dose of twice daily as an oral formulation at 35 mg/m²/day for Phase with dose escalation to 45mg/m²/day for 3 days. The dose expansion phase will be at the 45 mg/m²/day dose after safety and efficacy has been evaluated. The first administration of ATRA will be given in the morning, two days before the scheduled Dara infusion. The last administration of ATRA will be given in the evening of the day that Dara was administered (days -2, -1, and 1; day 1 is the day of Dara infusion).

ATRA-related toxicities

Subjects will be monitored for neurological symptoms and nutritional status. If Wernicke's encephalopathy is suspected, ATRA should be interrupted and parenteral thiamine should be initiated.

Pseudotumor cerebri

This complication has been mainly reported in patients aged <20 years and is characterized by presence of severe headache with nausea, vomiting, and visual disorders.

It is recommended to temporarily discontinue ATRA treatment and to administer opiates. As soon as the symptoms and the patient clinical conditions improve, the treatment with ATRA will be resumed at 50% of the previous dose during the first 7 days after the amelioration of pseudotumor cerebri. Thereafter, in absence of worsening of the previous toxicity, ATRA should be resumed at full dosage.

Table 8: ATRA Dose Reduction Steps

Dose Level	ATRA Dose reduction
Dose Level 2	45 (mg/m ²)
Dose Level 1 (Phase 1b starting dose)	35.5 (mg/m ²)
Dose Level -1	25 (mg/m ²)
Dose Level -2	20 (mg/m ²)

- ATRA will be discontinued for any Grade 4 non-hematologic toxicity.
- In the case of Grade 3 toxicity, ATRA should be held until the toxicity resolves to Grade ≤ 1 or baseline, at which time it may be resumed at a reduced dose.
- ATRA should be held for AST/ALT or alkaline phosphatase ≥ 5 x ULN and/or elevation of serum total bilirubin ≥ 3 x ULN. Upon resolution of hepatotoxicity, ATRA may be resumed at a reduced dose.

Treatment repeats every 28 days for at least 8 cycles in the absence of disease progression or unacceptable toxicity. Patients achieving stable disease may continue to receive treatment in the absence of disease progression or unacceptable toxicity.

After completion of the study treatment, patients are followed up at 28 days and then every 3 months for up to 12 months. Subjects will be evaluated for disease response during each cycle and at the end of study.

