3. STUDY ENDPOINTS

Primary Endpoints:

Phase 1b: The percentage of patients with treatment emergent adverse events (TEAEs) overall and per dose level.

- Patients with DLTs at each dose level.
- Patients with Grade ≥ 3 TEAEs
- Patient with serious adverse events (SAEs)
- Patients who discontinue because of TEAEs
- Patients with dose modifications (delays, interruptions, dose reductions)
- Clinically significant laboratory values

Phase 2: ORR as defined by IMWG criteria (subjects progressing on Dara + Len + Dex)

Secondary Endpoints:

- 1) ORR as defined by IMWG criteria (subjects progressing on Dara + Pom + Dex)
- 2) Rate of CR, sCR, or nCR
- 3) Rate of VGPR
- 4) TTP
- 5) DOR
- 6) PFS using Kaplan Meier
- 7) OS using Kaplan Meier

Exploratory Endpoints:

Explorative endpoints of samples collected before, during and after treatment with Dara + ATRA, + Pom + Dex and include but are not limited to the following:

- 1) Gut Microbiome analysis
- 2) Immune cell subset analyses
- 3) Analyses of cytokine, chemokine, inflammatory/anti-inflammatory and bacterial translocation markers
- 4) Basic peripheral blood laboratory variables
- 5) Genetic and epigenetic profiles

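### Table 4 gives two pomalidomide restart instructions for febrile neutropenia when G-CSF is continued, and does not say which governs

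*Combined protocol and SAP*

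**What the plan says.** Section 7.5, Table 4, has one neutropenia row. It names Grade 4 neutropenia (ANC below 500/µL) and then adds "or Febrile neutropenia (ANC" below 1,000/µL with a temperature criterion. The instruction beside both events has these parts:

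- Both events: "Withhold the dose and follow CBC weekly". G-CSF may be started at the treating physician's discretion.
- On resumption: "the dose of POM may be maintained if neutropenia was the only POM-related toxicity requiring a dose modification and GCSF treatments are continued".
- If those conditions are not met: "Otherwise, decrease by one dose level".
- Grade 4 neutropenia: ANC must be at least 500/µL to restart.
- Febrile neutropenia: ANC must be at least 1,000/µL to "restart pomalidomide dosing at 1 mg less than the previous dose".

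Footnote a to Table 4 adds: "If recovery from toxicities is prolonged beyond 14 days, then the dose of POM will be decreased by one dose level when dosing is restarted". Table 5 lists pomalidomide doses of 4, 3, 2 and 1 mg. Its footnote says "The minimum permitted dose level for POM is 1.0 mg" and rules out re-escalation. Section 4.1 lets patients enter at 4, 3 or 2 mg.

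Among the phase 1b primary endpoint items, Section 3 lists "Patients with dose modifications (delays, interruptions, dose reductions").

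**The concern.** The permission to keep the dose is written for the whole row and is not limited to patients without fever. The febrile sentence makes no exception for patients on G-CSF. A patient with febrile neutropenia who meets the G-CSF condition therefore falls under a permission to keep the dose and a direction to lower it, and nothing ranks one above the other.

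The condition can readily be met. Table 4 allows G-CSF to be started for the event itself, and Section 8.1 allows growth factors throughout and encourages myeloid growth factors when ANC is below 1,000/µL.

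This is an instruction that sites must follow when restarting a drug after a serious toxicity. The protocol summary lists two sites. If they read the row differently, the same event leads to different pomalidomide exposure for the rest of treatment, and any tabulation of reductions mixes a difference in reading with a difference in tolerability.

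**Working it through.** The plan gives no figure on this point to reproduce. The check sets the sentences side by side and lists the restart dose under each.

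**Inputs.** Rule A is the shared permission to keep the dose, with its fallback of one level down (Table 4). Rule B is the febrile sentence (Table 4). The other inputs are footnote a to Table 4, the dose steps and floor in Table 5, and the entry doses in Section 4.1. One dose level in Table 5 is 4 − 3 = 3 − 2 = 2 − 1 = 1 mg, so one level down and 1 mg less are the same step.

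**Step 1: where the rules differ in febrile neutropenia.**

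| Situation | Rule A | Rule B | Conflict? |
|---|---|---|---|
| Another pomalidomide-related toxicity requiring modification | 1 mg down (fallback) | 1 mg down | No |
| G-CSF not continued | 1 mg down (fallback) | 1 mg down | No |
| Recovery beyond 14 days | 1 mg down (footnote a) | 1 mg down | No |
| Sole toxicity, G-CSF continued, recovery within 14 days | Dose may be kept | 1 mg down | Yes |

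**Step 2: size in the conflicting case.**

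| Previous dose | Rule A, dose kept | Rule B | Difference as share of previous dose |
|---|---|---|---|
| 4 mg | 4 mg | 3 mg | 1/4 = 25% |
| 3 mg | 3 mg | 2 mg | 1/3 = 33% |
| 2 mg | 2 mg | 1 mg | 1/2 = 50% |

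Because re-escalation is not permitted, a patient reduced under rule B cannot later return to the dose that rule A would have kept.

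**Step 3: overlap of the two events.** A patient with ANC below 500/µL and a qualifying temperature meets both definitions in the row. That patient faces two ANC thresholds for restart (500 and 1,000/µL) as well as two dose rules.

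**Step 4: the phase 1b item.** It counts patients and pools delays, interruptions and reductions. The row withholds the dose in every case, which is already an interruption.

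- Pooled item: 1 patient under rule A (interruption); 1 patient under rule B (interruption and reduction). No change.
- Reductions counted alone: 0 under rule A; 1 under rule B.

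**Step 5: the 1 mg floor.** From 1 mg, rule B gives 1 − 1 = 0 mg, below the stated minimum. Every instruction in Table 4 to go down one level (thrombocytopenia, rash, other events) meets the same floor. This is a general gap in the table and not evidence for the neutropenia conflict.

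**The case against.** The strongest reply is that the sentences can be read together. The shared sentence is permissive, while the later one names a single event. A site that follows the febrile sentence breaches nothing in the permission, and a specific sentence is commonly read as overriding a general one. That reading is plausible and reduces the point from a flat contradiction to unclear precedence. It does not remove the point, because the table does not state the override or limit the permission to patients without fever. It also leaves the overlap case unsettled.

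The reply is also right that the scope is narrow: three conditions must hold together. The restart dose does not enter the DLT definition (Section 7.3), the escalation rule (Section 7.4) or the stopping rules (Section 9.4).

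A reader might draw three stronger conclusions that the documents do not support:

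- *The same event yields two counts in the phase 1b endpoint.* It does not. The item is pooled and the dose is withheld under either reading. The protocol specifies no separate count of reductions.
- *The conflict will arise often, given the 78% neutropenia rate in Section 4.2.* That figure is for neutropenia among Grade 3 toxicities in a trial of the backbone. It is not a febrile neutropenia rate, and none is given. Section 1.3 describes the common pomalidomide neutropenia as non-febrile.
- *The ORR result is affected.* Pomalidomide dose already varies by design at entry, and the documents give nothing from which an effect on response could be calculated.

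**Conclusion.** The point stands in a limited form. For febrile neutropenia as the only pomalidomide-related toxicity, with G-CSF continued and recovery within 14 days, Table 4 supports two restart doses that differ by 1 mg: 25%, 33% or 50% of a previous dose of 4, 3 or 2 mg. The difference is lasting. Outside those conditions the row is consistent about the size of the step.

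The consequence is operational and descriptive: inconsistent handling of a serious toxicity, and non-comparable figures if reductions or pomalidomide exposure are tabulated separately. The pooled phase 1b item, the ORR design, type I error and power are not affected. How often the case will arise is unknown.

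The conclusion assumes that the febrile sentence belongs to the same row as the shared instruction, as the table's layout indicates, and that no other text sets precedence. None was found in Section 7.5.

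**What to change.** The sponsor should reconcile the two sentences in the Table 4 neutropenia row so that Grade 4 neutropenia and febrile neutropenia each carry one restart instruction. The revised text should state:

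1. whether the G-CSF provision covers febrile neutropenia; and
2. which line, for both dose and ANC threshold, applies to a patient who meets both definitions.

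As a separate, general matter, Table 4 or Table 5 should say what applies when a reduction is called for in a patient already at the 1.0 mg minimum.

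The choice of rule belongs to the sponsor, and this review takes no position on it. The cost is protocol wording in one table row and one footnote. Sample size and the planned analyses do not change.

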This is a multi-institution phase 1b/2 study of ATRA in combination with fixed dose Daratumumab, Pomalidomide and Dex for patients with relapsed multiple myeloma who have progressed on the combination of Dara + Len + Dex. During the dose escalation phase (phase 1b) and after the first cycle, patients who have not experienced a drug-limiting toxicity (DLT), have not shown signs of progressive disease (PD), and in the opinion of the investigator would continue to benefit from additional Dara + Pom + Dex + ATRA may receive additional cycles of treatment (see section 7.4 for details). The phase 2 portion will allow further enrollment at the maximum tolerated dose (MTD) to further evaluate safety and efficacy.

Study Population

Patients with relapsed or refractory multiple myeloma who have progressed on the combination of Dara + Len + Dex or Dara + Pom + Dex. We will include a maximum of 42 patients (among 20-32 subjects previously exposed to Dara + Len + Dex or 10-22 subjects previously exposed to Dara + Pom + Dex).

Length of Study

The overall study duration is expected to be three (3) years, two years for enrollment, one year to complete follow-up.

Treatment Plan

During 28-day treatment cycles, patients will receive Dara 1800 mg subcutaneous (SC) administration at their current dose upon enrollment onto the study depending on their cycle. (If they are on cycles 1-2

then they will receive Dara 1800 mg SC days 1,8,15,22; if they are on cycles 3-6 they will receive Dara 1800 mg SC days 1 and 15; if they are on cycle 7 or beyond they will receive Dara 1800 mg SC on day 1).

Pomalidomide will be administered at the patient's currently tolerated dose (4,3, or 2 mg po daily) on days 1-21. Patients who are progressing on daratumumab + lenalidomide + dexamethasone will start with the 4 mg dose (standard of care starting dose) of pomalidomide.

Dexamethasone will be administered at 40 mg once weekly on days 1,8,15 for patients 75 years old and younger and at 20 mg once weekly on days 1,8,15 for patients older than 75. Patients may stay on their currently administered steroid regimen if it does not match the above.

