Factors that determine susceptibility of MM cells to Daratumumab include levels of target antigen CD38 and expression levels of the complement inhibitory proteins CD55 and CD59. Experiments with isogenic MM cell lines expressing different levels of CD38 revealed that the level of CD38 expression is an important determinant of Dara-mediated ADCC and CDC (Nijhof et al, 2015). At time of progression, there is a reduced level of CD38 on MM cells, whereas CD55 and CD59 are increased. In a cohort of 102 patients treated with Daratumumab monotherapy, pretreatment levels of CD38 expression on MM cells were significantly higher in patients who achieved at least a partial response (PR) compared with patients who achieved less than PR. CD38 expression was reduced in both bone marrow-localized and circulating MM cells, following the first Daratumumab infusion. CD38 expression levels on MM cells were again increased following Daratumumab discontinuation. In contrast CD55 and CD59 levels were significantly increased on MM cells at the time of progression (Nijhof et al, 2016). These preclinical and clinical data indicate that the downregulation of CD38 and the upregulation of CD55 and CD59 are involved in the development of Dara-resistant multiple myeloma.

All-trans retinoic acid (ATRA) has been shown in both cell lines and primary MM samples to increase CD38 expression levels and to reduce expression of the complement-inhibitory proteins CD55 and CD59(Nijhof et al, 2015). This resulted in significant enhancement of activity of Daratumumab in vitro and in humanized MM mouse models. Daratumumab and ATRA exhibit a strong synergy in MM cells derived from Dara-naïve patients and from patients with Dara-refractory disease, providing preclinical rationale for further evaluation of Daratumumab combined with ATRA in MM patients. Preliminary data from phase 1 trials combining Daratumumab and ATRA have shown that the combination is safe using ATRA 45 mg/m²/day dose.

It is our hypothesis that therapy with the addition of ATRA to the combination of Dara and Pomalidomide (Pom) with Dexamethasone (Dex) in patients progressing on Dara plus an IMiD + Dex will result in a significant clinical response. The aim of this study is to determine the ORR of Dara + Pom + Dex + ATRA in patients progressing on Daratumumab + Lenalidomide + Dex and to determine whether this combination is suitable for clinical use and evaluation in subsequent randomized trials. To this end, the ORR of Dara +

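### Section 7.5 fixes the ATRA expansion dose at 45 mg/m²/day, although phase 2 is meant to run at the MTD, which may be 35.5 mg/m²/day

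*Combined protocol and SAP*

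**What the plan says.** Three places in the protocol bear on the phase 2 ATRA dose.

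- **Section 7.5 (Dose Modification)**, in the ATRA paragraph after the dexamethasone tables: "The dose expansion phase will be at the 45 mg/m²/day dose after safety and efficacy has been evaluated".
- **Protocol Summary, Study Design**: "The phase 2 portion will allow further enrollment at the maximum tolerated dose (MTD) to further evaluate safety and efficacy".
- **Section 7.4**: the 3+3 escalation is run at 35.5 and then 45 mg/m²/day "to determine the MTD for further assessment in phase 2".

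Section 7.4 also sets the rules that decide which dose is the MTD. The definition is: "The MTD is defined as the highest dose with a cohort of 6 patients having no more than 1 patient with a DLT". A level can also fail early: "If 2 or more patients in a cohort of 3 patients exhibit a DLT, then that cohort will be deemed to have exceeded the MTD". There is a step back to the lower level, which begins "If the dose cohort below that at which the MTD is exceeded has enrolled only 3 patients" and goes on to require 3 more patients there. On the dose review, Section 7.4 adds: "All decisions will be documented in writing".

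**The concern.** The Protocol Summary and Section 7.4 make the phase 2 dose an outcome of phase 1b. Section 7.5 names it in advance. The two agree only if 45 mg/m²/day turns out to be the MTD. If it does not, the dosing section points to a level that the escalation section has found too toxic.

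ATRA is the drug being added to the daratumumab, pomalidomide and dexamethasone backbone, so its dose defines the phase 2 regimen. Section 7.5 also holds the table of ATRA reduction steps, so site staff will turn to it when dosing patients. The sections should not be able to give different answers.

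**Working it through.** **1. Does the expansion phase in Section 7.5 mean phase 2?** The term is not defined. The only other expansion in the protocol is the growth of a cohort from 3 to 6 patients in Section 7.4. That can happen at either level, so a fixed 45 mg/m²/day would not fit it. Phase 2 is the natural reading. Section 7.3 points the same way: it uses DLT-like events seen in phase 2 to judge whether the MTD suits later studies, which presumes that phase 2 is given at the MTD.

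**2. Can the MTD be 35.5 mg/m²/day?** Yes. There are two levels. If 45 mg/m²/day is exceeded, the level below is filled to 6 patients and qualifies with 0 or 1 DLT. The maximum of 2 × 6 = 12 patients agrees with the phase 1b maximum stated in Sections 4.1 and 9.2.

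**3. How often would 45 mg/m²/day fail once it is tested?** The plan states no figure to reproduce and gives no DLT rates. The true rate p is therefore an assumption, taken here as 10%, 20% or 30%.

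*Reading A: the top level must have 6 patients, as the MTD definition requires.* It fails with 2 or more DLTs in 6:

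P(fail) = 1 − (1−p)^6 − 6p(1−p)^5

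- p = 0.1: 1 − 0.531 − 0.354 = 0.114
- p = 0.2: 1 − 0.262 − 0.393 = 0.345
- p = 0.3: 1 − 0.118 − 0.303 = 0.580

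(Terms are rounded to three places; results come from unrounded values.)

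*Reading B: 0 DLTs in 3 suffices at the top level.* Section 7.4 does not explicitly say to fill that level after 0 of 3. The level then passes with 0 of 3, or with 1 of 3 followed by 0 of 3:

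P(fail) = 1 − [(1−p)^3 + 3p(1−p)^5]

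- p = 0.1: 1 − (0.729 + 0.177) = 0.094
- p = 0.2: 1 − (0.512 + 0.197) = 0.291
- p = 0.3: 1 − (0.343 + 0.151) = 0.506

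**4. How often would 35.5 mg/m²/day be the MTD, over the whole of phase 1b?** Under Reading A, let p1 and p2 be the true DLT rates at 35.5 and 45 mg/m²/day. The lower level must show at most 1 DLT in 6 and the upper level must fail:

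P(MTD = 35.5) = P(X ≤ 1 | 6, p1) × P(X ≥ 2 | 6, p2)

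For p1 = 0.1 and p2 = 0.2 this is 0.886 × 0.345 = 0.305.

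For 45 mg/m²/day to be the MTD, the lower level must first allow escalation and the upper level must then pass:

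P(MTD = 45) = [(1−p1)^3 + 3p1(1−p1)^5] × P(X ≤ 1 | 6, p2)

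For the same rates this is 0.906 × 0.655 = 0.594.

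| Assumed DLT rate at 35.5 / 45 | MTD = 45 | MTD = 35.5 | Neither qualifies |
|---|---|---|---|
| 5% / 10% | 86% | 11% | 3% |
| 10% / 20% | 59% | 31% | 10% |
| 10% / 30% | 38% | 51% | 11% |
| 20% / 40% | 17% | 50% | 33% |

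These figures treat 2 or more DLTs in 6 as exceeding the MTD. That follows from the MTD definition, although Section 7.4 states it outright only for a cohort of 3.

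**The case against.** The best defence is that the sentence is conditional. It places 45 mg/m²/day after an evaluation of safety and efficacy, and in this protocol that can be taken to mean the 3+3 and the team review in Section 7.4. On that reading, expansion goes ahead at the planned top dose if the dose clears. The clause does work as a loose gate. But it sets no criterion, does not mention the MTD and names no other dose, so it does not say what happens when 45 mg/m²/day fails.

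A second defence is that the rest of the protocol settles the matter. Dose selection belongs to Section 7.4, the Protocol Summary agrees with it, and dose decisions are put in writing. Section 9.4 adds stopping limits for phase 2, and Section 11.3 provides quarterly review by the data and safety monitoring committee. The sentence may be leftover text: the matching ATRA paragraph in Section 4.1 has no such sentence, and the one just before it in Section 7.5 is unfinished and gives the starting dose as 35 rather than 35.5 mg/m²/day. All of this stands and keeps the practical risk small. None of it corrects the sentence, and nothing in the protocol says that Section 7.4 overrides Section 7.5.

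Third, the Introduction says of 45 mg/m²/day: "Preliminary data from phase 1 trials combining Daratumumab and ATRA have shown that the combination is safe using ATRA 45 mg/m²/day dose". That statement covers daratumumab with ATRA and does not mention pomalidomide. Safety of the four-drug combination is the primary objective of phase 1b, so it cannot be assumed.

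Last, the probabilities rest on assumed DLT rates and do not measure harm. That is correct, and they are used here only to show that an MTD of 35.5 mg/m²/day is a realistic outcome.

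**Conclusion.** The inconsistency is real. Section 7.5 ties the expansion dose to 45 mg/m²/day, while the Protocol Summary and Section 7.4 tie it to an MTD that may be 35.5 mg/m²/day. Once 45 mg/m²/day has been tested, the chance that the sections disagree is 11%, 34% or 58% at true DLT rates of 10%, 20% or 30%. It is 9%, 29% or 51% if 0 of 3 is enough at the top level. The conclusion depends on reading the expansion phase as phase 2; the percentages also depend on the assumed DLT rates.

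The consequence is small, because the written decisions under Section 7.4 make it unlikely that a rejected dose would be given. It is still a contradiction in operative dosing text for the experimental drug, and it should be corrected.

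**What to change.** Replace the sentence in Section 7.5 with: *Phase 2 will use the MTD determined under Section 7.4 (45 or 35.5 mg/m²/day).*

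The cost is one sentence in the protocol. The sample size, alpha and power of the Simon design do not depend on it.

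Two neighbouring points could be settled in the same edit. The starting dose in the preceding sentence should read 35.5 mg/m²/day, as in Section 7.4 and the ATRA reduction table. The replacement sentence assumes that an MTD exists, so the sponsor may also wish to state what happens to phase 2 if neither level qualifies.
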